###### 2.2 Dietary factors associated with prostate cancer

Fats, Saturated Fat or High-Fat Foods: International comparison studies of per capita food disappearance have found correlations between diet and prostate cancer mortality of 0.39 for meat and 0.69 for animal fat. (4) Analytic epidemiological studies of the relationship between diet and prostate cancer have been less consistent. At least 15 case-control studies and 7 cohort studies have been conducted on the relationship between foods or nutrients and prostate cancer. (5 - 26) Fat, saturated fat, or foods high

in saturated fat (meat or dairy products) were found to significantly increase prostate cancer risk in about two-thirds of the case-control studies and two cohort studies.

Fruits, Vegetables, Dietary Fiber and Associated Nutrients: Previous research has not separated intakes of fruits, vegetables and dietary fiber and we must therefore consider them together. International comparison studies of per capita food disappearance have found correlations between cereals and prostate cancer mortality of -0.75. (4) About one-third of the case-control studies have found a protective effect of high frequency of vegetable intake,  $\beta$ -carotene intake, or vitamin C. (5-8, 10-19, 27) However other studies found a risk associated with high intakes of vitamin C or carotenes and one for fruit intake. (13, 19, 20, 36) Cohort studies provide more support with three of four studies reporting a protective effect of fiber-containing foods including green and yellow vegetables, rice, bread, beans/lentils/peas, fruits, nuts and tomatoes.

Mechanisms: Several mechanisms could explain a promotional effect of fat on prostate carcinogenesis, including effects on cell membrane composition, prostaglandin synthesis and hormone levels in blood or tissue. (29) Experimental studies suggest that low fat diets can alter the hormonal milieu in adult males. Fiber may act on hormone levels via its effect on the enterohepatic circulation of steroids. Dietary fiber may entrap steroids in the intestinal tract and prevent their reabsorption. (30)

### 3.0 METHODS

#### 3.1 Overview

This prospective cohort study of the relationships of diet, nutritional supplement use and obesity with the risk of prostate cancer. We are adding three sets of measures to the PCPT at the one-year post-randomization visit only: 1) usual dietary intake of macro- and micronutrients; 2) nutritional supplement use; and 3) adiposity, including distribution of adiposity. Principal study results will be based on analyses of 9,000 control group participants (specifically the 5,400 control group men who are expected to receive prostate biopsies at the end of the study. We will estimate the relative risk of histologically-proven prostate cancer using logistic regression models in which disease outcome at seven years is the dependent variable; the independent variable set consists of variables indicating level (categorized) of nutrient intake and covariates include confounding factors (e.g., total energy intake, age, race and family history of prostate cancer). Additional analyses will incorporate data from the intervention group to assess: 1) the relationship of diet with prostate cancer in persons treated with finasteride; and 2) the effect modification by diet of the relationship between finasteride and prostate cancer. We will validate dietary and nutritional supplement assessment instruments in a substudy of participants who will complete six, 24-hour dietary recalls over a one year period. Measures, questionnaires, quality control, validity studies and statistical analyses are described below.

Figure 1 shows a schedule of key measures for the PCPT (shown as O's) and for the diet study described here (shown as X's). Below we describe those measures related to the diet ancillary study.

#### 3.2 Diet Measurement

Selection of dietary assessment instruments: Assessment of nutrient intake in free-living populations is a difficult problem in epidemiologic research. There are no "gold standard" or criterion measures, and each of the standard methods (food diaries, dietary recalls, food frequency questionnaires) differs in reliability, accuracy, costs, participant burden and susceptibility to bias. In this study, we propose to use self-administered food frequency questionnaires for the following four reasons. First there is good evidence that FFQs can give reasonably valid estimates of the macronutrients (percent of energy from

fat, saturated fat, polyunsaturated fat), micronutrients (beta-carotene and vitamin C) and other dietary factors (fiber, usual servings of fruits and vegetables) of interest in this study. (31) Second, FFQs are the only dietary intake measure that minimizes the very high intra-individual, day to day variability in nutrient intake without using the average of multiple assessment (e.g., a 7-day food diary). Third, FEQs are the only practical approach to dietary assessment in very large, prospective studies. (32) For example, we estimate that adding two, four-day food records to this study would cost an additional 17.9 million dollars in direct costs. Fourth, FFQs have relatively low participant burden. Careful completion takes approximately 25 minutes and the quality control review takes only one to two minutes.

#### Description of Food Frequency Instrument

For this study, we propose to use a modification of the FFQ developed for the Women's Health Initiative. In format, this FFQ is based on the National Cancer Institute/Block FFQ, further revised for processing with the DataFax system. (33) The nutrient database used to convert food frequency information into nutrients is from the University of Minnesota's Nutrition Coding Center database, and the computer algorithms for analysis were developed at the Fred Hutchinson Cancer Research Center. (34) We have recently completed modifications of this FFQ for use in African-American, Latino and lower socioeconomic status populations in the "Women's Health Trial: Feasibility Study in Minority Populations" (WHT:FSMP).

#### Nutrient Analysis of FFQs

The nutrient database used by the FHCRC FFQ software is derived from the University of Minnesota Nutrition Coding Center nutrient database. The primary source for nutrient values in this database are the USDA Nutrient Database for Standard Reference (1987) and its periodic revisions. Our approach to generating an FFQ database is described elsewhere. (32) Table I gives the relevant variables that are calculated from this analysis system.

### 3.3 Nutritional Supplement Use

We will assess use of dietary supplements as part of the FFQ booklet. We will use a self-administered form to capture type, frequency and duration of supplements presently used. We will also collect data on use of other supplements during the previous five years, in order to better separate regular, long-term supplement users from others.

### 3.4 Anthropometry

The PCPT trial protocol includes assessments of height and weight at baseline, and weight at each subsequent annual visit. We will collect, at one year, four measures of body girth as measures of upper body obesity: abdomen, waist, hip and thigh circumferences. The motivation for measuring adiposity and the proposed measures of upper body obesity are described below.

Measures of adiposity: For epidemiologic studies, weight controlled for height and body mass index (the ratio of weight to height squared) are good, general indices of body adiposity and correlate well with more direct measures of total body fat mass such as underwater weighing. (29) In epidemiologic studies these measures predict many morbidity endpoints. (35) The pattern of distribution of adiposity has important metabolic consequences and distribution of fat predominantly in the abdominal region (so-called upper body obesity) may be more important in this study than total adipose mass. There is some controversy in the literature on the best measure of upper body obesity. While for women the ratio of waist to hip circumference appears to correlate well with biologic measures such as serum cholesterol, for men the ratio of waist to thigh may be superior. (36) In addition, for men measures at the waist (iliac crest) may underestimate upper body

fat. Because these measures are simple and non-invasive, we propose to measure both abdomen and waist and both hip and thigh circumferences.

Figure 1. Exposure and Covariant Assessments, Through Month 48 of PCPT

	Enroll- ment	Random- ization									Contin- uation to be propo- sed
	-3	0	3	6	9	12	15	18	21	24	48
ALL PARTICIPANTS											
Demographics											
Age, race, education	0										
Risk Factors											
Family and medical history, smoking, vasectomy, alcohol, physical and sexual activity	0										
Antropometry											
Height, weight	0					0					0
Waist, hip and thigh circumferences						X					
Serum											
PSA	0					0				0	0
Cholesterol	0										
Serum Bank	0					0				0	0
Nutrients											
Food frequency questionnaire						X					X
Nutritional supplement questionnaire						X					X
VALIDITY STUDY (SUBSAMPLE)											
Nutrients											
24-hour recalls							X	X	X	X	X
Food frequency questionnaire											X
Nutritional supplement questionnaire											X

X = Additions for Diet Study

0 = Part of PCPT protocol

### 3.5 Covariates

All covariates of interest for this study are collected as part of the PCPT protocol. These variables include: age, race, smoking and alcohol use; physical activity; education, family history of prostate cancer; participant history of chronic disease (cancer, cardiovascular disease, diabetes, hypertension), history and date of vasectomy; and PSA.

### 3.6 Validity Substudy

The purpose of validity research is to establish the measurement characteristics of the FFQ when used in the PCPT participant sample. We have sample data on the reliability and validity of similar FFQs when used in samples of women, but data on validity and reliability are more limited in men. Also, the PCPT will emphasize recruitment from a broad range of socioeconomic and racial groups, and it will be important to evaluate the FFQ's measurement characteristics more extensively in these populations. Finally, there is an agreement among nutritional epidemiologists that it is important to incorporate a substudy to evaluate the measurement characteristics of any dietary assessment tool when it is the sole measure of diet in a large epidemiologic study. (37) Such substudies can provide important support for the interpretation of study results.

Selection of Dietary Assessment Instrument: We will validate the PCPT FFQ against six, 24-hour dietary recalls. We selected dietary recalls instead of multiple-day food diaries for several reasons. First, 24-hour recalls can be administered over the telephone, so that collection and analysis in this multicenter trial can be centralized and standardized without having professional nutritionists at each clinical site. Second, nutrient intake assessment with the only alternative criterion measure, multiple-day diet records, requires extensive participant training and cooperation and carries a very high participant burden. Third and most importantly, 24-hour dietary recalls can be unannounced (not scheduled in advance), so that the bias towards temporary changes in diet due to record-keeping can be minimized. While participants could misreport their dietary behavior during a recall, they cannot change their behavior from the previous day. Finally, we believe that we can recruit a less biased sample of participants into the validity substudy using dietary recalls, because they need only respond to questions during 20 minute phone interviews and need not come to the clinic for training and then return for record reviews.

We plan a substudy in a random sample of 150 PCPT participants. We will administer six 24-hour recalls to each substudy participant, spread evenly between years one and two of the PCPT. Two of these recalls will be on Monday, to include weekend days and all recalls will be unscheduled. If a participant cannot complete a recall when contacted, we will make additional, unscheduled attempts. We expect to complete at least five recalls on 75 percent of the sample, which will yield 115 persons for analysis. At the end of the substudy protocol, we will compensate substudy participants \$100 for their time. Validity substudy participants will also complete an additional FFQ before the 24-month visit. This FFQ will cover the time period over the previous year, and serve as one of the comparison measures for the multiple, 24-hour dietary recalls. We will also use this FFQ to estimate the test-retest reliability, assuming that participants' diets should not change substantially over the one year time period.

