### **Validity Substudy: Data Analyses and Power**

Data Analyses. We will perform data analyses for the validity substudy on the combined sample of intervention and control men. We assume that, despite our concerns about inclusion of the intervention group in the main study, the drug will not affect accuracy of diet recall.

The data analyses and power calculations described below emphasize the estimation of the reliability and validity correlation coefficients and their lower bounds. This is because the goal of the validity study is to estimate with reasonable confidence the magnitude of the validity and reliability coefficients rather than simply whether the correlation coefficients differ from zero.

The analyses will be based on standard techniques for analysis of validity and reliability studies. (39, 40) Specifically, we will assess the reliability of the food frequency questionnaire by comparing the measures from the one-year post-randomization administration of the FFQ to the measures from the two-year administration of the FFQ, using the intraclass correlation coefficient. We will calculate intraclass correlation coefficients and their lower confidence bounds for each of the dietary measures listed in Table 1. In addition, we will divide participants into quartiles of intake based on the first and second FFQs and compare these using weighted kappa.

We will assess the validity (bias and precision) of FFQ measures by comparing the dietary measure from the average of the year 1 and year 2 FFQs ( $X_1$ ) to the measure from the combined six (or at a minimum five) 24-hour dietary recalls completed between year one and year two ( $X_2$ ). We will assess systematic bias in the FFQ (versus the recalls) as the difference between the mean FFQ measure in the substudy subjects and the mean measure from the six, 24-hour dietary recalls:  $X_1 - X_2$ . We will compute a confidence interval around this mean difference based on a one sample t-test on the variable  $X_{i1} - X_{i2}$  computed for each subject  $i$ . We will assess precision as the Pearson correlation coefficient between  $X_1$  and  $X_2$ , and its lower 95% confidence bound. We will estimate

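### The validity substudy's Monday rule records Sunday twice and secures no Saturday, and with no day weighting the imbalance is reported as questionnaire bias

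*Supplement*

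**What the plan says.** Appendix 19.7, section 3.6, sets out the substudy that serves Secondary Aim e, validation of the FFQ. On sample and schedule it says: "We plan a substudy in a random sample of 150 PCPT participants", and "We will administer six 24-hour recalls to each substudy participant, spread evenly between years one and two of the PCPT". On the days of the week there is one rule: "Two of these recalls will be on Monday, to include weekend days and all recalls will be unscheduled". The days of the other four recalls are not stated, and Sunday calls are neither required nor ruled out. Section 3.6 also makes clear which day a recall describes. In arguing that unannounced recalls limit reactive changes in diet, it says of participants that "they cannot change their behavior from the previous day".

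Missed calls are retried: "If a participant cannot complete a recall when contacted, we will make additional, unscheduled attempts". The expected yield is stated as: "We expect to complete at least five recalls on 75 percent of the sample, which will yield 115 persons for analysis".

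Section 3.9, under the substudy's data analyses and power, defines X1 as the average of the year 1 and year 2 FFQs. X2 is the measure from "the combined six (or at a minimum five) 24-hour dietary recalls completed between year one and year two". Systematic bias is the mean of X1 minus the mean of X2, with a confidence interval from a one-sample t-test; precision is the Pearson correlation of X1 with X2. No weighting of recalls by day of the week is described.

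**The concern.** The rule does not do what it is meant to do. It is there to bring weekend days, in the plural, into the reference measure, but a Monday call can reach only Sunday. Saturday enters only if some of the four unallocated calls happen to fall on a Sunday.

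The FFQ asks about usual intake over a year, so the recalls that serve as its yardstick should stand for a whole week. If intake on Saturday or Sunday differs from weekdays, an unbalanced set of days shifts X2 in every man in much the same way. That shift does not average out with more men. Because bias is defined as X1 minus X2, it is then read as a fault of the FFQ. Section 3.9 says the substudy's goal is to estimate the size of the validity and reliability coefficients with reasonable confidence, so a modest error in the reference is worth removing when removal is cheap.

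**Working it through.** **The plan's own figure.** Expected men with at least five recalls: 0.75 × 150 = 112.5, against the stated 115. The gap of 2.5 men in a projected yield is immaterial, and nothing below depends on it.

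**Inputs from section 3.6.** Six recalls per man; two on Monday; each recall covers the previous day; no day given for the other four. A calendar week gives each day 1/7 = 14.3% and the weekend 2/7 = 28.6%.

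**Day shares, six recalls.** Sunday is at least 2/6 = 33.3%, which is (2/6)/(1/7) = 2.33 times its calendar share, wherever the other four calls fall. For the rest, two patterns are considered:

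- Pattern A, the other four cover weekday intake only: Saturday 0%; weekend 2/6 = 33.3%.
- Pattern B, the other four fall evenly on the six non-Monday call days: Saturday (4/6)(1/6) = 11.1%; weekend 33.3% + 11.1% = 44.4%. A man then has at least one Saturday with probability 1 - (5/6)^4 = 52%.

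**Day shares, five recalls.** From the two Monday calls, Sunday carries at least 1/5 = 20% if one of them was missed, or 2/5 = 40% if another call was missed.

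**Effect on X2.** Set the weekday mean to 1, and let a and b be the proportional excess on Saturday and Sunday. With shares wSat and wSun,

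relative error in X2 = (1 + wSat·a + wSun·b) / (1 + a/7 + b/7) - 1.

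The documents give no day effects, so a and b are assumptions.

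| Assumed excess | Pattern A | Pattern B |
|---|---|---|
| Saturday and Sunday +10% | +0.5% | +1.5% |
| Saturday +20% only | -2.8% | -0.6% |
| Sunday +20% only | +3.7% | +3.7% |
| Alcohol-like: Saturday +50%, Sunday +50% | +2.1% | +6.9% |
| Alcohol-like: Saturday +100%, Sunday 0 | -12.5% | -2.8% |

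Two entries worked through: Saturday +20% only, pattern A, is 1/(1 + 0.20/7) - 1 = 1/1.0286 - 1 = -2.8%. Saturday and Sunday both +50%, pattern A, is (1 + 0.5/3)/(1 + 1/7) - 1 = 1.1667/1.1429 - 1 = +2.1%.

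For ordinary nutrients the error therefore runs from about -3% to +4%. For an item with a strong weekend pattern (Saturday +50 to +100%, Sunday 0 to +50%) it runs from about -12% to +2% in pattern A. Pattern B moves that range to about -3% to +7%. The direction depends on which weekend day is heavier and on days the plan leaves open.

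**The case against.** The strongest reply is that the four remaining days are unspecified, so Saturday is not excluded. In pattern B it gets 11.1% against 14.3%, and about half of six-recall men have at least one. In pattern A the weekend as a whole gets 33% against 29%, close to its due. Both observations are correct. They do not hold together, however: the weekend share is nearly right only where Saturday is missing altogether, and where Saturday is nearly right the weekend is over-weighted at 44%. The excess on Sunday for a six-recall man remains in either case. A reader might infer that Saturdays are never sampled; the text supports only that none is secured.

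A second reply is that little hangs on it, and much of that stands. This is a secondary aim of an ancillary study. The diet-cancer analysis in section 3.9 uses quartiles of FFQ intake and does not calibrate odds ratios with X2. A common shift in X2 moves no man between FFQ quartiles and, as a pure shift, leaves a Pearson correlation unchanged. Test-retest reliability compares the two FFQs and does not use the recalls.

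A reader might also infer from the five-recall minimum that the FFQ is judged only in the most compliant men. The documents do not support that. About three quarters are expected to qualify, further attempts are planned, men are compensated, and nothing shows that FFQ validity differs in those left out. A minimum also keeps an unadjusted reference comparably reliable across men. What can fairly be said is that no comparison of men with and without five recalls is described.

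**Conclusion.** The concern holds as a limited design point. The stated rule captures Sunday twice, secures no Saturday, and is not corrected by weighting. The over-weighting of Sunday among men with six recalls, 33.3% or more against 14.3%, follows from the text alone. The resulting error in the FFQ bias estimate rests on assumed day effects: a few percent for most nutrients, larger for something like alcohol, and of unknown sign. No effect on the correlation has been worked out. The trial's primary analysis and the diet-cancer odds ratios are untouched. The point is worth acting on because the remedy is specific and cheap, not because the error is shown to be large.

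**What to change.** In section 3.6, replace the two Monday calls with one unannounced call on a Sunday (Saturday intake) and one on a Monday (Sunday intake). Place the other four on Tuesday to Saturday (Monday to Friday intake), varying across men which weekday is left out.

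In section 3.9, define X2 as 5/7 of the man's weekday mean plus 2/7 of his weekend mean. With six recalls this gives Saturday and Sunday 1/7 each and each weekday recall 5/28.

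The five-recall minimum can stay. A man with five of the six still has at least one weekend and three weekday recalls, so both means exist. If a weekend call is the one missed, the other weekend day stands for both, so weekend calls deserve priority in the repeat attempts. As a check, compare baseline characteristics and FFQ values of men with and without five recalls.

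Cost: no extra calls, but some Sunday interviewing, and slightly unequal weights. If day-to-day variation is equal and independent across days, the variance of a six-recall mean rises from 1/6 = 0.1667 to 2(1/7)² + 4(5/28)² = 0.1684, about 1%. With five recalls it rises from 0.2000 to 0.2092 if a weekend call is missed (2/7 squared plus 4(5/28)²), or to 0.2109 if a weekday call is missed (2(1/7)² + 3(5/21)²), about 5% in each case.

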### 3.7 Endpoint

The endpoint for this study will be histologically -proven presence or absence of prostate cancer, assessed for most participants at the termination of the trial. The majority of prostate cancer cases detected will be asymptomatic.

### 3.8 Final sample and sample size

The control group is the primary group of interest for the proposed study of diet and prostate cancer. The intervention group is of less interest for several reasons: 1) finasteride may affect diet or weight, e.g., some hormone treatments lead to weight changes; and 2) if lower dietary fat intake and finasteride both reduce the risk of prostate cancer through hormonal mechanisms, there may be an interaction between the effect of diet and finasteride on prostate cancer. Although our primary analysis will be among control men, we will collect all measures on intervention and control groups given the blinded nature of the PCPT design. We do plan to analyze separately the results in the intervention group.

Only men with a positive biopsy before the end of the trial or a biopsy (positive or negative) at seven years will be considered to have endpoint information. The PCPT estimates that 5,400 (60%) of the 9,000 control men will have complete exposure and endpoint information. This is based on the following: 20% mortality (seven-year mortality of U.S. men age 55 - 70, median age 63); 15% loss to follow-up (our experience in the CARET trial); and 5% biopsy refusal at seven years.

